In the TFLs, subjects randomized to BKZ 160mg Q4W will be labeled as “BKZ 160mg Q4W”, subjects randomized to ADA 40mg Q2W will be labeled as “ADA 40mg Q2W” and subjects randomized to Placebo will be labeled as “Placebo / BKZ 160mg Q4W” (or “Placebo” when the TFLs report data from the DBP only).

For the ATP, all subjects on BKZ 160mg Q4W (that includes the subjects switching from Placebo at Week 16) will be labeled as “BKZ 160mg Q4W Total” in the TFLs.

Per protocol, visit windows of ± 2 days from the first dose at all visits through Week 16 and ± 3 days after Week 16 are permissible. For the SFU visit, the visit should occur no more than 3 days prior to the scheduled visit date and within 7 days after the scheduled visit date.

For the medical imaging collection date (at Week 16 and 52), the allowed visit window will be extended to ± 14 days around the scheduled visit date.

All by-visit tables will contain nominal (ie scheduled) visits only. Unscheduled visits will not be mapped to scheduled visits except for some assessments that may occur within the above visit window of a scheduled visit. In that case, the assessment will be mapped to the corresponding scheduled visit and will be used for the analysis unless data are present for that scheduled visit. Only data collected/mapped at the scheduled visits will be included in the analysis. The only deviation may concern unscheduled vendor data collected ([Section 10.5](#)).

Assessments collected at unscheduled and repeated visits will only be listed, except in the case of determining treatment-emergent markedly abnormal criteria for laboratory and vital sign parameters where all post-Baseline (scheduled and unscheduled) values will be used.

For by-visit tables summarizing efficacy data, the SFU visit will not be included but SFU efficacy data will be listed. By-visit tables summarizing safety data will however include the SFU visit. For PK, immunological and immunogenicity analyses, SFU data will be part of the data reported in some tables ([Section 9](#)).

A complete set of data listings containing all documented data and all derived data (eg, change from Baseline) will be generated.

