For subjects who switch treatment from placebo to BKZ at Week 16 (Visit 10), an additional Baseline value (called Week 16 Baseline) will be defined for efficacy variables. The Week 16 value will be considered as the Baseline value regardless of whether the Placebo subjects switched to BKZ on a later visit.

The variables listed below will be analyzed relative to the Week 16 Baseline value for the ATP, for timepoints after Week 16:

- PASI90 response
- ACR50 response.

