10.3 Clinical laboratory evaluations

The routine clinical laboratory evaluations specified below will be evaluated:

Table 10–2: Laboratory measurements

Hematology	Biochemistry	Urinalysis
Basophils	Calcium	pH
Eosinophils	Chloride	Albumin (protein)
Lymphocytes	Magnesium	Glucose
Monocytes	Potassium	Blood
Neutrophils	Sodium	Leukocyte esterase
Hematocrit	Glucose	Nitrite
Hemoglobin	BUN	Urine dipstick for pregnancy testing ^b
MCH	Creatinine	Urine drug screen ^c
MCHC	hs-CRP	
MCV	AST	
Platelet count	ALT	
RBC count	GGT	
WBC count	ALP	

Hematology	Biochemistry	Urinalysis
	Total bilirubin	
	Triglycerides ^a	
	Cholesterol ^a	
	HDL cholesterol ^a	
	LDL cholesterol ^a	
	LDH	
	Serum pregnancy testing ^b	

ALP=alkaline phosphatase; ALT=alanine aminotransferase; AST=aspartate aminotransferase; BUN=blood urea nitrogen; ET=early termination; GGT=gamma-glutamyl transferase; HDL=high density lipoprotein; hs-CRP=high sensitivity C-reactive protein; IMP=investigational medicinal product; IMS=International Menopause Society; LDH=lactate dehydrogenase; LDL=low density lipoprotein; MCH=mean corpuscular hemoglobin; MCHC=mean corpuscular hemoglobin concentration; MCV=mean corpuscular volume; RBC=red blood cell; SFU=Safety Follow-up; WBC=white blood cell

^a Biochemistry will include triglycerides, cholesterol, HDL cholesterol, and LDL cholesterol at Baseline, Weeks 12 and 24, and at the ET visit.

^b Pregnancy testing will consist of serum testing at the Screening visit for all women of childbearing potential. The pregnancy test will be urine at all other visits.

^c Urine drug screen will be performed at Screening visit.

Biochemistry and hematology values will be flagged based on their reference range:

- Values that are below the lower limit of the reference range will be flagged as 'L' (low)
- Values that are above the upper limit of the reference range will be flagged as 'H' (high)
- All other values will be referenced as normal.

Markedly abnormal values for blood chemistry and hematology will be defined as laboratory values graded 3 or 4 according to the Rheumatology Common Toxicity Criteria (RCTC). Definitions of the markedly abnormal values are given in [Table 10-3](#) and [Table 10-4](#) and are based on the RCTC units. All units in the tables below will be converted to the standard units based on Clinical Data Interchange Standards Consortium (CDISC) standards.

Table 10-3: Definitions of markedly abnormal biochemistry values

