Parameter name	Unit	Criteria	Abnormal designation
Creatinine	mmol/L	>3.0 x ULN or >3.0 x Baseline	AH
Glucose	mmol/L	<2.2 >13.9	AL AH
Calcium	mmol/L	>3.1 <1.75	AH AL
Magnesium	mmol/L	>1.23 <0.4	AH AL

Parameter name	Unit	Criteria	Abnormal designation
Potassium	mmol/L	>6.0	AH
		<3.0	AL
Sodium	mmol/L	>155	AH
		<130	AL
Triglyceride	mmol/L	>5.7	AH
Cholesterol	mmol/L	>10.34	AH

AH=abnormal high; AL=abnormal low; dL = deciliter; L = liter; mg = milligram; mmol = millimoles; ULN = upper limit of normal.

Table 10–4: Definitions of markedly abnormal hematology values

Parameter name	Unit	Criteria	Abnormal designation
Hemoglobin	g/L	<80	AL
		>40 above ULN or >40 above Baseline if Baseline is above ULN	AH
Lymphocytes Absolute	$10^9/L$	<0.5	AL
		>20.0	AH
Neutrophils Absolute	$10^9/L$	<1.0	AL
Platelets	$10^9/L$	<50	AL
WBC/ Leukocytes	$10^9/L$	<2.0	AL
		>100	AH

Table 10–5: Definitions of markedly abnormal liver enzyme elevation values

Parameter name	Unit	Criteria	Abnormal designation
Alkaline Phosphatase		>5.0 x ULN	AH
ALT	U/L	>5.0 x ULN	AH
AST	U/L	>5.0 x ULN	AH
Total Bilirubin	umol/L	>3.0 x ULN	AH
GGT	U/L	>5.0 x ULN	AH

ALT= alanine aminotransferase; AST = aspartate aminotransferase; GGT= gamma-glutamyltransferase

Definitions of the markedly abnormal values for liver enzyme elevation are given in [Table 10–5](#).

All laboratory summaries will be presented in standard international (SI) units and will be based on observed case values. In the case where laboratory values are below the LLOQ, then these will be set to the midpoint between 0 and the LLOQ for the purpose of summarizing the data.

In the case where laboratory data are expressed as above a fixed value (ie, “>xx.xx”), then the numeric portion of the value will be used (ie, xx.xx) to present and calculate statistics.

To define the minimum/maximum post-Baseline values, all post-Baseline assessments including those at unscheduled visits (but excluding any that occur more than 140 days after the last administration of study medication) will be used.

The following additional rule will be also applied :

Subjects who have completed PA0010 and have a PA0012 start date, only PA0010 results up to and including the PA0012 start date will be used to find the subjects minimum or maximum results. Additionally, subjects who are in PA0012 without a start date (date of first dose), only PA0010 results up to the Week 52 visit + 14 days will be used to find the subjects minimum or maximum results.

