The below results will be presented on the SS (for the DBP), on the ATS (for the ATP by treatment and for all BKZ-treated subjects), and on the AMS (for all the BKZ-treated subjects and on the ADA group). All values observed at any time while on treatment (ie, occurring at scheduled and unscheduled visits) will be included in the below tables. Baseline values and values observed more than 140 days after the last administration of study medication are not considered:

- Number and percentage of subjects with treatment-emergent markedly abnormal laboratory data overall (for blood chemistry and hematology), All values observed at any time while on treatment (ie, occurring at scheduled and unscheduled visits) will be included in this table summarizing markedly abnormal values. For this summary, Baseline values and values observed more than 140 days after the last administration of study medication are not considered.
- Number and percentage of subjects with markedly abnormal liver enzyme elevation tests (data beyond the CTCAE Grade 3 thresholds as outlined in [Table 10-5](#))

All laboratory data will be listed by treatment, subject and visit including changes from Baseline for numeric variables, flags for measurements outside the normal ranges, the relative study day, a flag for whether the test was not done and a flag for whether the subject was fasting.

The markedly abnormal laboratory data will also be listed separately.

Listings will also include Hepatitis B and C, human immunodeficiency virus (HIV), genomic proteomic/metabolomics, and genetic/epigenetic tests.

In addition, the laboratory results classified as Grade 3 or Grade 4 will be listed separately.

Urinalysis laboratory results and hepatic events will be listed separately.

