10.4 Vital signs, physical examination findings, and other observations related to safety

10.4.1 Vital signs and physical examination findings

The vital signs (systolic BP (mmHg), diastolic BP (mmHg), and pulse rate (beats/min)) will be summarized as:

- Absolute and change from Baseline at each scheduled visit on the SS for the full study period by randomized treatment
- For systolic and diastolic blood pressure, number and percentage of subjects experiencing at least one markedly abnormal value as defined in [Table 10-6](#).

Table 10-6: Definitions of markedly abnormal blood pressure values

Parameter (unit)	Markedly abnormal low	Markedly abnormal high
Systolic blood pressure (mmHg)	<90 and a decrease from Baseline of ≥ 20	>180 and an increase from Baseline of ≥ 20

Parameter (unit)	Markedly abnormal low	Markedly abnormal high
Diastolic blood pressure (mmHg)	<50 and a decrease from Baseline of ≥ 15	>105 and an increase from Baseline of ≥ 15

For the Baseline visit where several BP assessments are taken, the individual observed data assessments as well as the mean of these assessments will be summarized and listed (pre-dose, 30 min post-dose and 1-hour post-dose).

Treatment-emergent markedly abnormal values will be analyzed on the SS (for the DBP, by treatment), on the ATS (for the ATP by treatment and for all BKZ-treated subjects), and on the AMS (for all BKZ-treated subjects and the ADA group).

Vital signs measurements will also be listed by visit and timing relative to dosing including changes from Baseline. The listing will also include details of abnormal value based on flags as defined in [Table 10-6](#) ("L" for markedly abnormal low and "H" for markedly abnormal high).

Similarly, physical examination findings together with the details of abnormalities (when applicable) will be listed by treatment group, subject and visit.

Body weight will be only listed.

10.4.2 **Electrocardiograms**

The following ECG variables will be assessed at Baseline (Screening visit), Week 16, Week 52 and at the end of SFU:

- Heart Rate (bpm)
- PR interval (ms)
- RR interval (ms)
- QRS duration (ms)
- QT interval (ms)
- QTcF interval (ms)
- QTcB interval (ms)

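### The treatment-emergent markedly abnormal laboratory table has no emergence condition, and abnormalities that began on placebo are counted under BKZ after the Week 16 switch

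*SAP*

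**What the plan says.** Section 10.3 plans a table of "Number and percentage of subjects with treatment-emergent markedly abnormal laboratory data overall" for blood chemistry and hematology, for three periods: the Double-Blind Treatment Period (DBP) on the Safety Set, the ATP on the Active Treatment-Blind Set, and the AMP on the Active Medication Set. What is counted is stated broadly: "All values observed at any time while on treatment (ie, occurring at scheduled and unscheduled visits) will be included in the below tables". What is left out is stated next: "For this summary, Baseline values and values observed more than 140 days after the last administration of study medication are not considered". Section 3.1 gives the same convention, using all values after Baseline when "determining treatment-emergent markedly abnormal criteria for laboratory and vital sign parameters where all post-Baseline (scheduled and unscheduled) values will be used".

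The criteria are severity thresholds: "Markedly abnormal values for blood chemistry and hematology will be defined as laboratory values graded 3 or 4" on the rheumatology toxicity scale, set out in Tables 10-3 and 10-4.

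Section 3.3 anchors Baseline to the first injection of study drug, whether or not it is active. For placebo subjects who move to BKZ, "an additional Baseline value (called Week 16 Baseline) will be defined for efficacy variables". Nothing equivalent is defined for laboratory values or vital signs.

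Section 10.4.1 uses the same label for blood pressure: "Treatment-emergent markedly abnormal values will be analyzed on the SS (for the DBP, by treatment"), and then for the ATP and AMP. Table 10-6, however, requires both a threshold and a change from Baseline.

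**The concern.** Elsewhere in the safety section the term means something else. Section 10.2 makes an adverse event treatment-emergent by its onset at or after first dosing, and assigns it to a period by its date of emergence. An adverse event that began on placebo is therefore not a new BKZ event. A laboratory abnormality that began on placebo and is still there after Week 16 is.

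At stake is the accuracy of the safety columns, above all BKZ 160mg Q4W Total. For placebo-randomized subjects, Section 3.6.5 defines the AMP as the ATP alone. Their post-switch values enter the BKZ column with no check on where they stood when BKZ started. These tables belong to the Week 24 analysis, which Section 4.3.1 says supports a marketing application. Grade 3 or 4 counts are usually small, so a few misattributed subjects can be noticeable.

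**Working it through.** The SAP gives no rate on this point, so the check is of wording and criteria.

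**Step 1. Does any criterion exclude a pre-existing abnormality?**

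| Table | Directional criteria | Count |
|---|---|---|
| 10-3 | creatinine 1, glucose 2, calcium 2, magnesium 2, potassium 2, sodium 2, triglyceride 1, cholesterol 1 | 13 |
| 10-4 | hemoglobin 2, lymphocytes 2, neutrophils 1, platelets 1, leukocytes 2 | 8 |
| Both | 13 + 8 | 21 |

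Of the 21, 19 are absolute limits with no Baseline term. Two mention Baseline:

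- Creatinine high is ">3.0 x ULN or >3.0 x Baseline". The Baseline limb is an alternative, so it adds a way to qualify. A subject above three times the upper limit of normal (ULN) on Day 1 and again later still qualifies on the first limb.
- Hemoglobin high is more than 40 g/L above ULN, or more than 40 g/L above Baseline when Baseline exceeds ULN. Read literally, the first limb still catches a persistent abnormality. But if Baseline > ULN, then Baseline + 40 > ULN + 40, so the second limb adds nothing under that reading. The intent may be that Baseline replaces ULN as the reference, in which case this one criterion would exclude a stable pre-existing value.

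So 20 of 21 criteria on any reading, and 21 of 21 on the literal one, let a pre-existing abnormality count as emergent once it is recorded again.

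**Step 2. Day 1 abnormalities.** A subject with triglycerides above 5.7 mmol/L on Day 1 and again at Week 12 is reported as emergent. The rule is the same for placebo, BKZ and ADA, and Day 1 status is a pre-randomization characteristic. The effect is a wrong label and inflated absolute rates, not a shift between arms by design.

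**Step 3. Abnormalities arising on placebo.** Three provisions combine:

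- Baseline is the Day 1 value (Section 3.3).
- The Week 16 Baseline is limited to efficacy variables (Section 3.3).
- Only ATP values count for placebo-randomized subjects in the AMP (Section 3.6.5).

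A value that crosses the threshold on placebo and is recorded again after Week 16 is therefore counted under BKZ. Nobody switches from placebo to ADA, so the ADA column has no counterpart.

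**Step 4. The switch day.** Section 2.3.2.3 puts the first ATP dose after all Week 16 assessments, yet the DBP ends and the ATP begins on that day. Section 10.2 allocates same-day adverse events to a period; Section 10.3 has no such rule for laboratory values. A pre-dose Week 16 sample could be placed in either period.

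**Step 5. Blood pressure.** Table 10-6 requires a change of at least 20 mmHg (systolic) or 15 mmHg (diastolic) from Baseline as well as a threshold. A reading that was extreme on Day 1 and stays stable does not count. For switchers the reference is still Day 1, so a qualifying change that occurred on placebo and persists is counted in the ATP and AMP.

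**Step 6. Size.** Section 2.3.1 plans 420 BKZ and 280 placebo subjects. BKZ Total is then at most 420 + 280 = 700, of whom 280/700 = 40% are switchers. The one-sided part is bounded by 280. Purely as an illustration, if 1% to 3% of switchers carried a placebo-era abnormality into the ATP (an assumption with no source in the SAP), the count would be 280 × 0.01 = 2.8 to 280 × 0.03 = 8.4, or about 3 to 8 subjects.

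**The case against.** The strongest reply is that Section 3.1 states the convention openly: any on-treatment value counts. On that view the table is a disclosed tally under a loose label, and the exclusion sentence is itself proper, since a Baseline record should not count as an on-treatment event. That is fair as far as it goes. The fault is the comparison that is missing, not the sentence. But a reader of the output sees the label, and the label claims emergence.

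Second, the information is partly visible elsewhere: changes from Baseline by visit, CTCAE shift tables, listings, and a separate Placebo / BKZ column in the ATP table. This helps with Day 1 abnormalities. It does not help with the switch, because the shift tables run over the DBP and ATP together, and the AMP table shows BKZ only as a pooled column (Table 4-4).

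Third, these are descriptive counts, and the error overstates harm on BKZ rather than hiding it. That stands and limits the severity.

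A reader might also infer more than the SAP supports:

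- That liver results such as GGT are affected. Table 10-5 feeds a separate summary that is not labelled treatment-emergent.
- That randomization fails to balance the whole problem in the ATP and AMP. Day 1 abnormalities are balanced in expectation, apart from dropout, and also enter the ADA column. Only placebo-era abnormalities are one-sided.
- That the SAP uses a Week 16 reference for efficacy alone. Sections 9.1 and 9.2.1 use the Week 16 pre-dose sample as Baseline for pharmacokinetics and antidrug antibodies in this group. The gap is specific to laboratory values and vital signs.
- That every earlier abnormality is charged to BKZ. It counts only if an abnormal value is recorded again in the period.

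**Conclusion.** The point holds in two parts of different weight. The chemistry and hematology table is called treatment-emergent without any condition that the abnormality emerged; this inflates absolute rates in all arms and is balanced in expectation. Separately, abnormalities that began on placebo and are recorded again after Week 16 are attributed to BKZ in the ATP and AMP tables. This part is asymmetric, applies to blood pressure as well, and concerns at most 280 subjects.

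The number affected cannot be derived from the SAP. It depends on how often grade 3 or 4 values occur and persist, and on eligibility limits that are not in this document. It would be tempting to apply an assumed 1% to 3% to all 700 BKZ-treated subjects and report 7 to 21 wrongly counted. That would mix the balanced Day 1 part with the switcher part and rest on a rate with no source. Efficacy conclusions are untouched. The correction is worth making because it is cheap and the tables support a submission.

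**What to change.** In Section 10.3, for Tables 10-3 and 10-4, count a value as treatment-emergent only if the last available value before the first dose of the relevant treatment was not markedly abnormal in the same direction. The reference value is:

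- the Day 1 Baseline, for the DBP and for subjects who do not switch;
- the last value up to and including the Week 16 pre-dose sample, for placebo switchers in the ATP and AMP. It must be the last available value rather than the Week 16 value, because Table 10-2 schedules lipids at Baseline and Weeks 12 and 24 (and early termination). For lipids the scheduled reference is Week 12.

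In Section 10.4.1, measure the Table 10-6 blood pressure change for switchers in the ATP and AMP from that same pre-switch value. In both sections, assign Week 16 pre-dose samples and readings to the DBP.

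Keep the all-values count as a second row titled post-Baseline markedly abnormal, which also preserves comparability with tables produced under the current rule.

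The cost is a few sentences and one flag in the laboratory and vital-sign datasets. The small downside is that worsening from grade 3 to grade 4 appears only in the second row and the shift tables.

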10.4 Vital signs, physical examination findings, and other observations related to safety

10.4.1 Vital signs and physical examination findings

The vital signs (systolic BP (mmHg), diastolic BP (mmHg), and pulse rate (beats/min)) will be summarized as:

- Absolute and change from Baseline at each scheduled visit on the SS for the full study period by randomized treatment
- For systolic and diastolic blood pressure, number and percentage of subjects experiencing at least one markedly abnormal value as defined in [Table 10-6](#).

Table 10-6: Definitions of markedly abnormal blood pressure values

Parameter (unit)	Markedly abnormal low	Markedly abnormal high
Systolic blood pressure (mmHg)	<90 and a decrease from Baseline of ≥ 20	>180 and an increase from Baseline of ≥ 20

Parameter (unit)	Markedly abnormal low	Markedly abnormal high
Diastolic blood pressure (mmHg)	<50 and a decrease from Baseline of ≥ 15	>105 and an increase from Baseline of ≥ 15

For the Baseline visit where several BP assessments are taken, the individual observed data assessments as well as the mean of these assessments will be summarized and listed (pre-dose, 30 min post-dose and 1-hour post-dose).

Treatment-emergent markedly abnormal values will be analyzed on the SS (for the DBP, by treatment), on the ATS (for the ATP by treatment and for all BKZ-treated subjects), and on the AMS (for all BKZ-treated subjects and the ADA group).

Vital signs measurements will also be listed by visit and timing relative to dosing including changes from Baseline. The listing will also include details of abnormal value based on flags as defined in [Table 10-6](#) ("L" for markedly abnormal low and "H" for markedly abnormal high).

Similarly, physical examination findings together with the details of abnormalities (when applicable) will be listed by treatment group, subject and visit.

Body weight will be only listed.

10.4.2 **Electrocardiograms**

The following ECG variables will be assessed at Baseline (Screening visit), Week 16, Week 52 and at the end of SFU:

- Heart Rate (bpm)
- PR interval (ms)
- RR interval (ms)
- QRS duration (ms)
- QT interval (ms)
- QTcF interval (ms)
- QTcB interval (ms)

The date and time of the ECG will be recorded in the eCRF together with the Investigator interpretation and details of any abnormalities. A summary of the number and percentage of subjects with normal, abnormal not clinically significant, and abnormal clinically significant ECG results will be presented for Baseline, Week 16, Week 52 timepoints and at end of SFU.

Absolute values at Baseline, Week 16, Week 52 and end of SFU and change from Baseline at Week 16, Week 52 and at end of SFU of all ECG variable will also be summarized.

QTc outliers are defined as QTcF/QTcB values following dosing that are > 450 ms or that have increased from Baseline > 30 ms. These outliers will be summarized in a dedicated table using the following categories:

- Value > 450 ms, > 480 ms, > 500 ms
- Increase from Baseline > 30 ms, > 60 ms, > 90 ms

- Value >450 ms and increase from Baseline >30 ms, value >500 ms and increase from Baseline >60 ms.

Number and percentage of subjects who meet the ECG outlier criteria defined above at Week 16, Week 52 and end of treatment will be summarized.

All ECG tables will be provided on the SS by randomized treatment.

All 12-lead ECG data where QTcF and QTcB outliers are highlighted will also be listed.

